5. AMENDMENTS AND UPDATES

None.

6. MILESTONES

Milestone	Planned date
Completion of feasibility assessment	October 15, 2019
Start of data collection	August 10, 2020
End of data collection	January 22, 2022
Interim study report (ex-Italy)	July 22, 2021
Final study report	May 26, 2022 ^e

^e Anticipated date; subject to change based on the impact of the COVID-19 pandemic on the availability of members of ethics review committee, staff at the institutional review board, and site staff.

7. RATIONALE AND BACKGROUND

7.1. Study Background

Invasive aspergillosis and mucormycosis are rare, life-threatening fungal infections associated with high mortality.^{1,2} Causative agents for fungal infections can vary across geographic locations; however, *Aspergillus fumigatus* and *Rhizopus arrhizus* are associated with the majority (approximately 70%) of invasive aspergillosis and mucormycosis cases, respectively.¹ Although the epidemiology of rare fungal diseases is not well studied, the incidence rates (per 100,000 persons) for invasive aspergillosis and mucormycosis are estimated to be 4.6 and 0.09 in the UK, 2.8 and 0.04 in Spain, and 1.8 and 0.1 in France, respectively.² Incidence rates are difficult to estimate due to a lack of a reliable denominator.^{2,5}

Cresemba® (isavuconazole) is an antifungal agent that contains the active substance isavuconazole. Its mechanism of action involves blocking the production of a key component of the cell membrane of fungi, thus weakening the membrane and preventing fungal cell growth.³ Isavuconazole can be administered orally or by infusion. Isavuconazole demonstrated non-inferiority compared to voriconazole with improved safety profile in the SECURE clinical trial for patients with invasive aspergillosis (phase 3, randomized, double-blind, comparative-group; NCT00412893).⁴ Isavuconazole was approved by the EMA on October 15, 2015, for use in adults for the treatment of (i) invasive aspergillosis and (ii) mucormycosis in patients for whom amphotericin B is inappropriate.

7.2. Invasive Aspergillosis

Invasive aspergillosis usually occurs in immunocompromised patients with hematological malignancies, oncology patients receiving chemotherapy, and immunosuppressed patients (eg, as a result of taking immunosuppressive drugs after transplant surgery). Other risk factors include comorbidities such as diabetes, renal or liver dysfunction, chronic obstructive pulmonary disease, and neutropenic sepsis. Patients with comorbidities also are at higher risk for stays in the ICU.⁶ Diagnosis of invasive aspergillosis is typically made by the combination of host status, imaging, and mycological findings.¹ Treatment of invasive aspergillosis usually includes antifungal medications such as voriconazole or isavuconazole.¹

The SECURE clinical trial (NCT00412893) was a phase 3 randomized, double-blind, comparative-group study designed to compare the efficacy and safety of isavuconazole vs. voriconazole in the treatment of patients with invasive aspergillosis. The primary outcome measure was all-cause mortality at day 42. In the intention-to-treat population, all-cause mortality was 19% for isavuconazole and 20% for voriconazole, adjusted treatment difference = -1.0% (95% CI: -7.8, 5.7).⁴ Patients treated with isavuconazole also had a lower frequency of hepatobiliary disorders (9% vs. 16%; $P = 0.016$), eye disorders (15% vs. 27%; $P = 0.002$), and skin or subcutaneous tissue disorders (33% vs. 42%; $P = 0.037$). Additionally, treatment-related AEs were reported in 42% and 60% of patients receiving isavuconazole and voriconazole, respectively ($P < 0.001$). Guidelines therefore recommend isavuconazole and voriconazole for first-line treatment of invasive aspergillosis.

7.3. Mucormycosis

The main risk factors for mucormycosis include diabetes mellitus, hematological malignancies, stem cell/organ transplantations, corticosteroid therapy, and neutropenia.² Mucormycosis is usually diagnosed through identification of causative agents by histopathological analysis of tissue specimens, in patients showing symptoms of the infection.¹ However, diagnosis is challenging, and cultures are only occasionally positive. Initial treatment of mucormycosis typically includes surgery to remove infected tissues and antifungal treatment with amphotericin B.¹

The VITAL clinical trial (NCT00634049) was a single-arm, open-label trial, that included an assessment of the efficacy and safety of isavuconazole for treatment of mucormycosis in 37 patients. The primary outcome was independent data review committee-determined overall response (complete or partial response [treatment success] or stable or progressive disease [treatment failure]) at day 42, day 84, and end of treatment. The results demonstrated that by day 42, 11% of patients had a partial response, 43% had stable disease, 3% had disease progression, 8% had missing assessments, and 35% had died.⁷ The efficacy of isavuconazole and amphotericin B was also compared in a matched case-control analysis.⁷ At day 42, all-cause mortality was similar in cases with isavuconazole as the primary treatment and amphotericin B-treated matched controls (weighted all-cause mortality: 33% vs. 41%; $P = 0.595$).⁷

Although the use of some antifungals are restricted in patients with renal impairment, in a pooled analysis of the SECURE and VITAL trials, isavuconazole was reported to be well tolerated in patients with renal impairment.⁸

7.4. Study Rationale

Isavuconazole obtained market authorization in the US and the EU in 2015. The generation of RWE will provide additional insight into isavuconazole use and related outcomes in clinical practice. The current study is a retrospective cohort study based on a multi-country chart review to be conducted in five European countries (France, Germany, Italy, Spain, and the UK), designed to obtain RWE of isavuconazole patterns of use, clinical response, HCRU, and safety in clinical practice.

8. RESEARCH QUESTION AND OBJECTIVES

Primary objectives:

- To document real-world clinical outcomes (all-cause mortality, overall response) of isavuconazole in patients with invasive aspergillosis or mucormycosis receiving treatment in routine clinical practice in Europe (France, Germany, Italy, Spain, and the United Kingdom).
- To assess real-world safety (isavuconazole-related AEs and SAEs) of isavuconazole in patients with invasive aspergillosis or mucormycosis receiving treatment in routine clinical practice in Europe.

Secondary objectives:

- To describe demographic and clinical characteristics of patients with invasive aspergillosis or mucormycosis receiving isavuconazole in routine clinical practice in Europe.
- To document treatment patterns among patients with invasive aspergillosis or mucormycosis receiving isavuconazole in routine clinical practice in Europe.
- To quantify HCRU among patients with invasive aspergillosis or mucormycosis receiving isavuconazole in routine clinical practice in Europe.

9. RESEARCH METHODS

9.1. Study Design

This is an observational retrospective cohort study involving the review and abstraction of pertinent data from the medical records of patients diagnosed with invasive aspergillosis or mucormycosis who received treatment with isavuconazole (index event) between October 15, 2015, and June 30, 2019.^f The target sample size for this study is approximately 600 patients (with a minimum of 200) across 22 sites located in Europe.^g

De-identified data (ie, anonymous to non-site staff) on patient demographics, disease characteristics, isavuconazole treatment patterns, clinical response, safety outcomes, and HCRU will be collected from patient medical records and entered into an EDC system by site staff between August 2020 and March 2021 for Germany, Spain, and the UK, and between October 2021 and January 2022 for Italy.^h The differences in the data abstraction timelines are due to ethics and contracting processes in Italy taking between 6 to 12 months to complete, compared with an estimated maximum of 4 months in the remaining countries. As this study is retrospective, information pertaining to patient care will already be documented in patient medical records at the time of chart abstraction.

A steering committee composed of experts within hematology and infectious diseases will provide input and guidance on the study design and implementation, as well as the interpretation of results.

^f The eligibility period end date is subject to change based on timing of medical record abstraction and anticipated number of potentially eligible patients during the proposed eligibility timeframe.

^g Dependent on interest in participation and the number of eligible patients each site can contribute, the total number of sites enrolled as well as patients per site could increase/decrease.

^h Dates of medical record abstraction are subject to change based on the volume of potentially eligible patients during the timeframe of the current eligibility period and the timing of study start-up.

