9.3.1.3. Data Collection (Chart Abstraction) Periods

Patients who initiate isavuconazole treatment (index event) during the eligibility period (October 15, 2015, to June 30, 2019)^m will be identified and screened for inclusion/exclusion criteria for enrollment into the study.

[figure not shown]
The two main study periods for data collection from each patient's medical chart are:

- **Pre-index event period:** Baseline data on demographics and medical history will be collected based on all available information in medical records before the index event.

^m The eligibility period end date is subject to change based on timing of medical record abstraction and anticipated number of potentially eligible patients during the proposed eligibility timeframe.

- **Post-index event period:** The timeframe for follow-up data collection will begin one day post-index treatment initiation and end at the earliest of the following: 6 months after post-index treatment discontinuation, death, or loss to follow-up, or December 31, 2019 (see [Figure 1](#) and [Figure 2](#)). Key timepoints of interest for assessment of clinical response and safety will be at 6 weeks, 12 weeks, and 24 weeks after initiation of index treatment (see [Figure 2](#)).

Figure 2. Data Collection Periods and Timepoints for Each Patient

FU = follow up.

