9.4.3. Clinical Effectiveness

Category	Variable	Timepoint
Clinical response ⁿ	Date of assessment (DD MMM YYYY) Clinical response status documented in the medical chart: 
• Clinical response;• Clinical failure;• Unknown.	Post-index period
Re-activation of same or new infection	Re-activation documented in the medical chart: 
• Yes;• No. Assessment date (DD MMM YYYY)	Post-index period
Radiological assessments	Radiographic assessment date (DD MMM YYYY) Radiographic examination type: 
• Chest X-ray;• CT scan;• Ultrasound;• MRI;• Other (specify);• Unknown. Radiographic examination location 
• Brain;• Lungs;• Liver;• Kidney;• Stomach;• Intestines;• Other (specify);• Unknown.	Post-index period
Radiological response ^o	Radiological examination date (DD MMM YYYY)	Post-index period

ⁿ Clinical response will be evaluated according to the following mutually exclusive modalities: Clinical response: resolution or partial resolution of all attributable clinical symptoms and physical findings. Clinical failure: no resolution of any attributable clinical symptoms and physical findings and/or worsening. When medical record documentation is not clear for the abstractor on which categories to specify, the investigator should review all available medical record documentation to determine classifications. If the investigator determines there is not enough medical record documentation to make the classification, they will indicate unknown. Since clinical response classification is important to the study, participating sites will be selected for participation in the study based on reporting to have diligent medical record documentation for response.

^o Radiological response will be evaluated according to the following criteria: Radiological response: ≥ 50% improvement from initial assessment, or improvement of at least 25% from the initial assessment for the follow-up at 6 weeks (ie, Day 42 [\pm 14 days]) or if end of treatment occurred before this time. When medical record documentation is not clear for the abstractor on which categories to

Category	Variable	Timepoint
	Radiological examination type 
 • Chest X-ray; • CT scan; • Ultrasound; • MRI; • Other (specify); • Unknown. 	

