9.9.2. Planned Analysis

9.9.2.1. Analysis Plan for Primary Objectives

Mortality/survival rates will be summarized and reported. Clinical, radiological, and mycological response documented in the medical record will be summarized using proportions and counts for each category. Details of radiological and mycological assessments will be reported in a descriptive manner, including the type of assessment and the assessment findings. Definitions of response will be provided in the SAP. Time to response and all-cause mortality will be analyzed using the KM method and quartiles and 95% CIs will be reported.

Descriptive statistics will be used to describe all AEs and SAEs reported during the medical record review. The safety data described will include event type, relationship to isavuconazole treatment (where known), event severity, event seriousness, action taken with isavuconazole treatment and outcome of the event. Definitions of AEs and SAEs will be described in the SAP. Time from index treatment to first AE onset will be summarized.

Key timepoints of interest for assessment of treatment effectiveness, safety and survival outcomes will be at 6 weeks, 12 weeks, and 24 weeks after initiation of index treatment. In the cases that usual care visits do not directly coincide with these timepoints, the time windows for assessment of outcomes will be defined in the SAP.

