### 6.3 ANALYSIS OF CLINICAL OUTCOMES

Each clinical outcome will be analyzed using counts and frequencies at weeks 6, 12, and 24, along with other descriptive information about the clinical outcome itself.

Additionally, time-to-event analyses anchored on the index date of isavuconazole initiation will be performed using the KM method. For each clinical outcome, the time-to-event analyses will result in a KM plot with summary statistics, including survival-time quartiles and KM estimates at weeks 6, 12, and 24 with accompanying 95% CIs. All analyses will be performed for invasive aspergillosis patients, mucormycosis patients, and for the total study population. If subgroup analyses are pursued, Cox regression will be employed to derive HRs and accompanying 95% CIs.

For the death outcome, patients will be categorized as dead, alive, or unknown at each timepoint of interest, and primary cause of death will be tabulated (Appendix 1, Analysis Table 5.1). For KM analyses, a documented death will comprise the event, and patients will be censored at the date when they are last known to be alive (Appendix 1, Analysis Figure 1; Appendix 1, Analysis Table 5.2).

For the clinical response outcome, patients will be categorized as having clinical success, having clinical failure, or unknown response at each timepoint of interest will be tabulated (Appendix 1, Analysis Table 6.1). In addition, rates of reactivation of the same infection and rates of new infection will be documented overall and specific to whether these events occurred during isavuconazole treatment. For KM analyses, clinical response will comprise the event, and patients will be censored at the earliest timepoint of any of the following: loss to follow-up, end of study, or death (Appendix 1, Analysis Figure 2; Appendix 1, Analysis Table 6.2).

For radiological response, patients will be categorized as having a success, not having a response, unknown response, or not applicable (for the first assessment) at the relevant timepoints of interest (Appendix 1, Analysis Table 7.1). Additionally, radiological examination type and bodily location of the examination will be tabulated. For KM analyses, radiological response will comprise the event, and patients will be censored at the earliest timepoint of any of the following: loss to follow-up, end of study, or death (Appendix 1, Analysis Figure 3; Appendix 1, Analysis Table 7.2).

PFIZER CONFIDENTIAL

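### Unclear responses are classified at abstraction with no limit on how late the evidence may be, so hindsight can enter the week 6 and week 12 response rates

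*Protocol*

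**What the plan says.** Protocol section 9.1 gives the setting: because the study is retrospective, "information pertaining to patient care will already be documented in patient medical records at the time of chart abstraction". Beyond that, two descriptions of where a response comes from stand in the plan.

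**The chart states it.** In protocol section 9.4.3 the clinical variable is labelled "Clinical response status documented in the medical chart". Section 9.9.2.1 plans that "Clinical, radiological, and mycological response documented in the medical record will be summarized using proportions and counts for each category".

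**The investigator assigns it.** Footnotes n (clinical), o (radiological) and p (mycological) to section 9.4.3 cover charts the abstractor finds unclear. There, "the investigator should review all available medical record documentation to determine classifications". The fallback is narrow: "If the investigator determines there is not enough medical record documentation to make the classification, they will indicate unknown". SAP section 5, Table 1, repeats the rule for all three responses.

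On timing, SAP section 6.3 says: "Each clinical outcome will be analyzed using counts and frequencies at weeks 6, 12, and 24". It also plans Kaplan-Meier analyses with response as the event. Protocol section 9.9.2.1 promises that "the time windows for assessment of outcomes will be defined in the SAP", but the SAP gives a window only for week 6 radiology (day 42 ± 14 days). The one outer limit is the end of data collection, in protocol section 9.3.1.3: the earliest of "6 months after post-index treatment discontinuation, death, or loss to follow-up, or December 31, 2019". The SAP's version (section 4.2) leaves out the calendar date.

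**The concern.** Overall response is part of a primary objective, and the protocol abstract names clinical, mycological and radiological response as its parts. If an unclear week 6 chart is resolved by someone who can see how the patient fared afterwards, the code may reflect the later course rather than the state at week 6. A survivor may drift towards success and a patient who died towards failure. The week 6 and week 12 rates, and the time-to-response curves, would then carry information from after the timepoint they claim to describe. A larger sample would not reduce this. Unless the origin of each response is recorded at abstraction, the analysis data set cannot show afterwards how many were affected.

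**Working it through.** **1. Is later information in front of the classifier?** The last eligible initiation is 30 June 2019 and data collection starts on 10 August 2020, more than 13 months later (protocol sections 6 and 9.3.1.2). Date and cause of death are abstracted from the same charts (sections 9.3 and 9.4.5). No blinding is mentioned.

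**2. Does the data-collection cap protect week 6?** Suppose the cap also bounds the review. A patient starting on 30 June 2019 has 184 days to 31 December 2019. After week 6 that leaves 184 − 42 = 142 days of later record, and after week 12 it leaves 184 − 84 = 100 days, unless death or loss to follow-up comes first. The cap does not protect either timepoint.

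**3. Are unclear cases likely?** Protocol section 9.11 expects gaps, including in radiological and mycological response at end of treatment. The clinical definition creates more. Success requires at least partial resolution of every attributable finding; failure means that none resolved, or that there was worsening. A patient with some findings better and others unchanged fits neither.

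**4. Which components are exposed?** Radiology has numeric thresholds (50%, or 25% at week 6 or at an earlier end of treatment) and a week 6 window, so it is less exposed. Clinical response and presumed eradication rest on judgement and are more exposed.

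**5. Size.** The plan has no figure for this. Its only precision table (protocol Table 1) can be used to check the interval formula. The Wilson width is 2z√(p(1−p)/n + z²/4n²)/(1 + z²/n). With p = 0.19 and n = 292, 237, 152 and 106 it gives 8.98, 9.96, 12.41 and 14.83 points, against 9.0, 10.0, 12.5 and 15.0 stated. The table reproduces.

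For the bias, every input is an assumption:

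- R, true week 6 response: 50%.
- S, later survival: 0.5 × 0.85 + 0.5 × 0.60 = 72.5% if responders and non-responders survive at 85% and 60%; or 0.5 × 0.80 + 0.5 × 0.30 = 55% if at 80% and 30%.
- u, share of responses that are unclear; h, share of those coded by eventual survival. The rest are taken as coded correctly.

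Shift = u × h × (S − R):

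| u | h | u × h | S − R = 22.5 points | S − R = 5 points |
|---|---|---|---|---|
| 10% | 50% | 0.05 | +1.1 | +0.3 |
| 20% | 50% | 0.10 | +2.3 | +0.5 |
| 40% | 50% | 0.20 | +4.5 | +1.0 |
| 20% | 100% | 0.20 | +4.5 | +1.0 |
| 40% | 100% | 0.40 | +9.0 | +2.0 |

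The sign is not fixed. With survival of 80% and 30%, S = 0.30 + 0.50R, which falls below R once R exceeds 60%. With 85% and 60%, S = 0.60 + 0.25R, which falls below R once R exceeds 80%. Beyond those points the shift is negative.

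For scale, the Wilson 95% half-width at a 50% response rate is 4.0 points for n = 600, 6.9 for n = 200 and 15.3 for n = 37.

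**The case against.** The strongest reply is that the rule is attached to dated records. Section 9.4.3 collects an assessment or examination date with each response, so an investigator could naturally read it as asking for everything relevant to that assessment. Nobody is told to use survival, which is a separate variable. There are safeguards too: escalation from abstractor to investigator, an unknown code, and selection of sites for good response documentation. This is a fair reading, but it is not the only one. The text does not limit the evidence, and the unknown code applies only after the full record has been searched.

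Second, the variable list in section 9.4 is expressly not exhaustive, and neither the CRF nor the SAP table shells can be seen here. A provenance field may exist. That part is conditional; the missing evidence limit is not, because it concerns the definition itself.

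Third, the amounts are assumptions. This stands in full. The 9.0-point figure, and 4.5 at u = 20%, need every unclear case to be coded purely by survival.

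A reader might also infer that the protocol contradicts itself, with section 9.1 promising that outcomes are already classified. It does not: that sentence concerns information about patient care, and classifying from existing records is compatible with it. Nor is a distorted association between response and mortality at stake in the planned outputs, since SAP section 6.3 analyses each outcome separately.

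**Conclusion.** The point holds as a gap in the outcome definitions. The plan describes response as charted, allows unclear responses to be assigned at abstraction without an evidence cut-off or blinding, and analyses both kinds together. Hindsight bias in the week 6 and week 12 rates is possible, chiefly for clinical response and presumed eradication.

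The documents do not show that bias will occur, how large it would be or which way it would go. Under the assumptions above it ranges from about 0.3 points, well inside sampling error, to several points, which could match or exceed the 4.0-point half-width at n = 600. It would be wrong to conclude that the response rates will be inflated by a known amount, or that all three components are equally affected. The case for acting is that this is a primary outcome, the remedy is cheap, and the origin of each response has to be recorded at abstraction.

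**What to change.** 1. In footnotes n, o and p of protocol section 9.4.3, and in SAP Table 1, limit the evidence for an unclear response to documentation of the patient's status at or before the response assessment date. Allow later-dated reports, letters or discharge summaries that describe that same assessment. Where this is not enough, code unknown.
2. Add one CRF item per response, unless it already exists: *stated in the chart* or *assigned by the investigator at abstraction*. Defining it by what the chart says, not by who wrote it, keeps it usable where the investigator also treated the patient.
3. In SAP section 6.3, tabulate response by this item and repeat the week 6, 12 and 24 rates with chart-stated responses only.

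The cost is one tick box per response record, one sentence in each definition, one extra table and more unknown responses; how many more cannot be judged from the documents. Charts that state a response may differ from those that do not, so a gap between the two sets of rates would signal sensitivity to the assigned responses and would not by itself prove hindsight.
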